Aim 2: Isolate the Neurobiological Basis of the "Loss" Research Domain Criteria (RDoc) and the Change Associated with Treatment. Using a factor analysis of the HDRS, we have previously demonstrated that the "loss" RDoC criteria is significantly correlated to MRGlu in frontal cortical areas. We therefore hypothesize that change in MRGlu (pre to post treatment) in these regions will be correlated with symptom improvement specifically in "loss" symptoms. As an exploratory extension, we will determine whether these changes are treatment-specific (i.e. to SSRI or placebo). A validation of our hypothesis suggests a targeted mechanism of action, and provides

a significant step forward for precision treatment. If regional changes in MRGlu are not correlated to improvement in this RDoC category, it suggests that SSRI (or placebo) induced changes may be a downstream effect that should be examined further.

Aim 3: Validate NonInvasive Full Quantification of MRGlu Using Simultaneous Estimation. Full quantification of brain MRGlu with FDG (as performed in this study) requires measuring FDG in arterial plasma (input function) from arterial catheter insertion and blood analysis. This costly and invasive procedure creates a barrier to widespread PET use. Our group has developed an innovative method for Simultaneous Estimation (SimE) of input information and PET outcome measures (e.g., MRGlu). SimE fully quantifies brain MRGlu without requiring an arterial catheter. In the case of FDG, our data suggests that SimE used with a single venous sample can provide accurate results. We further hypothesize that the venous sample may be entirely replaced by study data (e.g., injected dose) and biometrics (e.g., body surface area, lean body mass index). Using two different approaches (statistical imputation and physiological parametric modeling) and previously collected data, we will train the SimE for accurate quantification in the absence of blood data. The rich data collected in this study will then provide a robust benchmark for validation of the SimE approach.

B. BACKGROUND AND SIGNIFICANCE:

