Simultaneous Estimation Anchor: SimE has been recognized as a promising approach for noninvasive PET, as it works for several tracers used in neuroreceptor studies. By itself, however, SimE does not obviate the need to draw blood during the scan. To ensure model identifiability, at least one blood sample must be taken and used as an individual. We hope to be able to eliminate this single blood draw, which would help reduce barriers to widespread PET use.

C. RESEARCH DESIGN AND METHODS

1. Research Site

The PET/MRI scans will be performed at the Imaging Center (Ambulatory Care Pavilion) at the Stony Brook University Hospital.

2. Study sample

N = 120 (diagnosed with MDD) will be enrolled to obtain 100 subjects who complete the protocol

Age range: 18 years and above.

We anticipate the sample will comprise approximately equal numbers of males and females. No ethnic/racial/gender group is excluded.

3. Recruitment Methods

 Advertisements (flyers, brochures): Subjects will be recruited through response to advertisements, including local newspapers, on Craigslist and other websites. Approved fliers will be distributed around Stony Brook campus, other campuses, off campus locations such as health fairs and places of worship (with permission), and via letters from OPD to patients on their waitlist. Texts of advertisements and other materials to be distributed in recruitment efforts will be submitted to the IRB for approval before they are prepared for distribution. The use of websites and newspapers will allow us to target a broader range of the population.

- 2. Subjects will be recruited through lists obtained from the electronic medical record and provided to the study team by Research Services. The information we will receive for each patient include: MRN, patient age, name of treating physicians/nurses, date of most recent encounters, prescribed medication, diagnostic code with its corresponding official description and a free text description. Our study coordinators and clinician will have access to the data. Our team would contact the treating physician of potential participants through letter or telephone call. We will then ask the treating physician to provide information about our study to the patient, or ask the patient if we may contact him or her with more information.

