Image Processing: After MRI and PET processing is performed, the data will be processed using the semi-automated analysis pipeline developed in CUBIT. MRI processing includes segmentation (grey, white, csf) and parcellation into different regions of interest. PET processing includes motion correction, coregistration to the MRI, determination of regional activity over time (time activity curves) and modeling of the time activity curves. The modeling requires information about the radioactivity of plasma during the scan. These techniques have been previously described. (Parsey, Ogden et al. 2010, Miller, Hesselgrave et al. 2013) Using this analysis, the metabolic rate of glucose (MRGlu) can be calculated. The arterial input function (as well as Simultaneous Estimation, for comparison) will be used to derive the regional MRGlu.

E. STATISTICS

Aim 1: Correlation between HDRS and pretreatment MRglu will be determined in the ESC and placebo treatment groups in the three specified regions. In post hoc analysis, spatial resolution will be improved through examination of correlation between whole brain voxel MRglu and HDRS using SPM8 on aligned voxel based parametric images. Our group has extensive experience performing these analyses. For both analyses, outcome possibilities include: differential treatment Δ HDRS prediction (i.e. significant correlation, with different sign for placebo and ESC; significant correlation, within different regions, for placebo and ESC; significant correlation in same region, same direction); or insignificant correlation with HDRS for both treatments. The former outcomes would be immediately clinically significant and applicable. The final option, though unlikely based on preliminary data, would also be an important finding and suggest that, either the cohort should be expanded, or additional imaging/clinical measures are needed for prediction.

The power analysis was performed with an estimated 50 subjects per treatment. With a cohort of 50 subjects (on SSRIs), we can detect a true correlation as low as 0.39, with 80% power (two-tailed analysis, Δ = 0.05). In our FDG treatment study, the observed R2 value was 0.32, meaning the true correlation between the data was 0.57 (significantly higher than 0.39). However, this is almost certainly an overestimation because only the voxel cluster highly correlated to the outcome was chosen (as in all cited studies).

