Aim 2: The change in MRgIu from pre to post treatment (SSRI and placebo) will be calculated in the midbrain cluster defined by our preliminary studies. The correlation between this value and Δ HDRS will be assessed with both SSRI and placebo groups as well as with separate cohorts, to determine if there is an effect of treatment. As with Aim 1, a post hoc analysis will also be performed examining this correlation over all voxels.

Power Analysis. The partial correlation for each cluster and the factor related to "loss" varies between 0.5 and 0.6, meaning the true correlation ranges between 0.71 and 0.77. Based on this, using a single cohort (n=50), a true correlation as low as 0.39 can be detected with 80% power (two-tailed analysis, Δ =0.05).

When cohorts are combined (n=100 completers, of 120 enrollees), a correlation as low as 0.27 can be detected.

Aim 3: In a previous cohort, we investigated SimE performance with FDG (and four other tracers). The optimal timing for the blood sample used to anchor the FDG SimE estimation was found to be 40 minutes after injection. At this time, FDG venous and arterial samples are essentially interchangeable. Results using this 40-minute blood-based anchor show that SimE-derived MRGlu are close to MRGlu derived using arterial sampling-based estimation: slope 0.730, correlation 0.955 with compartmental analysis slope 0.876, correlation 0.974 with Patlak analysis. Validation: Validation will be considered complete when MRGlu using conventional (Patlak) analysis and arterial samples matches MRGlu calculated with SimE and one venous sample in the proposed study data. The threshold will be a correlation of at least 0.95 and slope of 0.85 in at least 30 subjects.

F. FUNDING STATUS

This study will be funded through the National Institute of Mental Health (R01MH104512-01A1; 1123782-1-70976), the DANA Foundation (Coeus Proposal #20458, PN15125265; 1128493-1-73073), the Brain and Behavior Research Foundation, (Grant #24459; 1134680-1-75849), internal funding from the Department of Computer Science and pilot funding provided by the Department of Radiology for PET/MRI scan costs.

G. DATA and SAFETY MONITORING PLAN (for more than minimal risk studies)

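### Aim 2's combined-arm correlation has no term for randomised arm, so arm mean differences can create or mask the association it tests

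*Combined protocol and SAP*

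**What the plan says.** E. STATISTICS, Aim 2 takes the pre-to-post change in MRGlu in a midbrain cluster and correlates it with Δ HDRS. This "will be assessed with both SSRI and placebo groups as well as with separate cohorts, to determine if there is an effect of treatment". Two analyses are therefore planned: one across both randomised arms and one within each arm.

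The power paragraph covers both. For a single cohort of 50, "a true correlation as low as 0.39 can be detected with 80% power (two-tailed analysis, Δ =0.05"; the last symbol is evidently alpha. It then adds: "When cohorts are combined (n=100 completers, of 120 enrollees), a correlation as low as 0.27 can be detected". The Aim 1 power text gives the split: "The power analysis was performed with an estimated 50 subjects per treatment".

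A. SPECIFIC AIMS, Aim 2 states the hypothesis without reference to arm: "change in MRGlu (pre to post treatment) in these regions will be correlated with symptom improvement specifically in" loss symptoms. Treatment specificity comes second: "As an exploratory extension, we will determine whether these changes are treatment-specific (i.e. to SSRI or placebo").

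No arm covariate, arm-adjusted partial correlation or arm-by-MRGlu interaction is named for Aim 2. The only partial correlation mentioned there belongs to the earlier data behind the power paragraph.

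**The concern.** Change in MRGlu and Δ HDRS are both outcomes of randomised treatment. If escitalopram moves both relative to placebo, the two arms form two clouds with different centres. A correlation across all 100 patients then mixes two things: whether patients whose metabolism changed more also improved more, and whether the drug shifted both averages. Only the first is a patient-level link between metabolism and symptoms.

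The error can run either way. Shifts that line up can produce a significant combined result with no within-arm association. Shifts that oppose the within-arm slope can cancel a real one. The combined analysis has the larger sample and the smaller detectable correlation, so its result will carry weight.

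The plan also looks for a treatment effect by setting the combined and separate-arm correlations beside each other. Finding significance in one arm and not in the other is not a test of whether the arms differ.

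**Working it through.** **Inputs from the plan.** 50 completers per arm, 100 combined, two-sided alpha 0.05, 80% power, stated detectable r of 0.39 (n=50) and 0.27 (n=100).

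**Inputs assumed.** Arm differences d1 (change in MRGlu) and d2 (Δ HDRS), in within-arm SD units. The documents give no arm means or SDs, so a range is used.

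**Step 1: the plan's own figures.** By Fisher z, r_min = tanh((1.960 + 0.842)/√(n−3)).
- n=50: tanh(2.802/√47) = 0.387 (stated 0.39).
- n=100: tanh(2.802/√97) = 0.277 (stated 0.27; a noncentral-t calculation gives 0.272). Power at r=0.27 is about 78%.

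The stated figures reproduce, apart from slight optimism at n=100. They apply to a correlation with no arm term.

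**Step 2: what combining the arms does.** At 1:1 allocation the arm indicator has variance 1/4. The combined covariance is r_within + d1·d2/4 and the variances are 1 + d1²/4 and 1 + d2²/4, so

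r_combined = (r_within + d1·d2/4) / √((1 + d1²/4)(1 + d2²/4)).

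Example with r_within = 0 and both shifts 0.8: 0.16/1.16 = 0.138. Example with r_within = 0.28 and shifts 0.5 and −0.5: (0.28 − 0.0625)/1.0625 = 0.205.

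**Step 3: rejection rates.** 40,000 simulated trials of 50+50 per row, two-sided 5% tests:

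| Within-arm r | Shift HDRS / MRGlu (SD) | Combined r | Rejects, no arm term | Rejects, arm term |
|---|---|---|---|---|
| 0 | 0.3 / 0.3 | 0.02 | 5.6% | 5% |
| 0 | 0.3 / 0.5 | 0.04 | 6–7% | 5% |
| 0 | 0.5 / 0.5 | 0.06 | 8–9% | 5% |
| 0 | 0.5 / 0.8 | 0.09 | about 15% | 5% |
| 0 | 0.8 / 0.8 | 0.14 | 28% | 5% |
| 0.28 | 0 / 0 | 0.28 | 81% | 81% |
| 0.28 | 0.5 / −0.5 | 0.20 | 54% | about 81% |
| 0.28 | 0.5 / −0.8 | 0.16 | 36% | about 81% |
| 0.27 | 0.5 / 0.5 | 0.31 | about 90% | 78% |

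To produce r = 0.27 from arm means alone, equal shifts of √(4×0.27/0.73) = 1.22 SD on both measures are needed.

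**Step 4: cost of an arm term.** One degree of freedom: tanh(2.802/√96) = 0.278, against 0.277.

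**Step 5: comparing the two arms.** The detectable difference in Fisher z between two groups of 50 is 2.802 × √(2/47) = 0.578. If one arm's correlation is 0, the other must be tanh(0.578) = 0.52.

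**The case against.** The strongest reply is that the same sentence plans separate-arm correlations, which arm mean shifts cannot distort. A combined result driven only by arm means would usually sit beside two null arm results: in the five zero-correlation rows above, a significant combined test together with at least one significant arm occurred in only 3–4% of trials. That mitigation is real. It is incomplete, because each arm alone detects only r of about 0.39 and the plan gives no rule for reading the three results together.

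Second, the shifts are assumed. At 0.3 SD or less on both measures the distortion is negligible, and nothing in the documents says that shifts would oppose the within-arm slope. This stands as a limit on the size of the problem.

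Third, if the drug relieves symptoms through metabolism, the between-arm component is part of the signal and the marginal correlation is truly non-zero. That is fair, and calling a rejection false presumes a within-arm question. But an unadjusted correlation cannot separate such mediation from two unrelated drug effects.

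Two stronger readings are tempting and unsupported. A reader might infer that the combined correlation is the main test of Aim 2, so that Aim 2 as a whole has an uncontrolled error rate. The documents name no primary Aim 2 analysis, and the power text gives the single cohort first. A reader might also infer that a positive combined correlation is to be taken as mechanism, since A. SPECIFIC AIMS says "A validation of our hypothesis suggests a targeted mechanism of action". That sentence concerns frontal regions and loss symptoms, whereas the analysis in E. STATISTICS uses a midbrain cluster and Δ HDRS.

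**Conclusion.** The point holds for the combined n=100 correlation: as specified, it mixes within-arm association with differences between arm means. How much this matters depends on shifts that the documents do not give. It is negligible at 0.3 SD or less on both measures, moderate near 0.5 (8–9% rejection against a nominal 5%), and serious at 0.8 (28%). Masking of a real association is equally possible in principle, with power falling from 81% to 54% or 36% under the opposing shifts tried. All these figures assume 50 completers per arm and equal within-arm spread.

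The separate-arm correlations are unaffected, and the stated detectable correlations are not materially wrong. The defect lies in how the combined analysis, and the treatment comparison drawn from it, are specified. The change is worth making because the flaw is certain in form, uncertain in size and cheap to remove.

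**What to change.** In E. STATISTICS, Aim 2:

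- Define the combined analysis as the partial correlation of change in MRGlu with Δ HDRS given randomised arm, that is, the MRGlu-change coefficient in a regression of Δ HDRS on change in MRGlu plus arm.
- Base the n=100 detectable figure on that model (0.278 by Fisher z).
- Keep the separate-arm correlations, and say which Aim 2 analysis is confirmatory.
- For the exploratory treatment-specificity question, add the arm-by-MRGlu-change interaction. State that it has 80% power only for a Fisher-z difference of about 0.58, for example r = 0.52 against 0. It is needed because an arm main effect does not reveal arms with correlations of opposite sign, an outcome that the Aim 1 text already foresees.

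The cost is a few sentences and one degree of freedom for the arm term, plus one more in the interaction model; no extra patients or scans. There is one genuine trade-off: the adjusted test no longer counts between-arm covariation as evidence, so it rejects less often when the shifts align with the within-arm slope (78% against about 90% at 0.5/0.5 SD with within-arm r = 0.27). If the investigators want that component, it should be reported separately as a difference between arms.

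### Aim 2's exploratory question of treatment-specificity is answered only by symptom correlations; no analysis compares MRGlu between the randomised arms, and none tests whether the correlation differs by arm

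*Combined protocol and SAP*

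**What the plan says.** Section A, Aim 2, sets a correlational main hypothesis: change in MRGlu in frontal cortical regions goes with improvement in loss symptoms. It then adds: "As an exploratory extension, we will determine whether these changes are treatment-specific (i.e. to SSRI or placebo"). If no correlation is found, "it suggests that SSRI (or placebo) induced changes may be a downstream effect".

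Section E, Aim 2, is the only analysis text for this aim. MRGlu change "from pre to post treatment (SSRI and placebo) will be calculated in the midbrain cluster defined by our preliminary studies". The correlation of that change with HDRS change is to be examined in the two groups together "as well as with separate cohorts, to determine if there is an effect of treatment". Finally, "a post hoc analysis will also be performed examining this correlation over all voxels". Power is given for a single correlation only: 0.39 with one cohort of 50 and 0.27 with both cohorts combined.

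Section D states that patients are randomised by the pharmacy with researchers blinded, and that both arms are scanned at week 8. No section compares MRGlu between the arms, gives an interaction, or tests the difference between the two correlations.

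**The concern.** The treatment-specificity question can be read in two ways, and the plan has a test for neither.

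- **Does escitalopram change MRGlu more, or less, than placebo does?** This concerns a difference in means between randomised arms. Adding a constant to every MRGlu change in one arm leaves that arm's correlation with HDRS change exactly as it was, so the per-arm correlations cannot see it. The pooled correlation can move, but it then blends a difference between arms with the association between individuals.
- **Does the link between MRGlu change and HDRS change differ by arm?** This needs a direct comparison. Finding one correlation significant and the other not is not such a comparison.

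At stake is the mechanistic reading of Aim 2. Section A counts the absence of a placebo comparison among the limits of earlier FDG studies and calls the placebo effect an obstacle to evaluating mechanism. The design supplies the comparison, but the written analysis does not use it for MRGlu. Followed as written, it could miss a real effect of the drug on metabolism or suggest treatment-specificity where there is none.

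**Working it through.** **Inputs.** 50 subjects per treatment (section E, Aim 1); 100 completers, two-sided 0.05 and 80% power (section E, Aim 2). The documents give no mean, SD or pre-post correlation for MRGlu, so shifts and correlations marked as assumed below are mine.

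**1. The plan's own figures.** Fisher z: r = tanh((1.960 + 0.842)/√(n − 3)).
- n = 50: tanh(2.802/√47) = 0.387; the plan says 0.39.
- n = 100: tanh(2.802/√97) = 0.277; the plan says 0.27. Power at 0.27 is 77.8% by Fisher z and 79.3% by noncentral t.

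The figures reproduce, apart from what looks like truncation in the second. Each is power for one correlation against zero, not for any comparison of arms.

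**2. How the planned correlations behave.** 8,000 simulated trials per scenario, 50 per arm, normal data with unit SDs.

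| Assumed truth | ESC r significant | Placebo r significant | Arms disagree | Pooled r significant | Between-arm t-test on MRGlu change | Direct test of two correlations |
|---|---|---|---|---|---|---|
| ESC shifts MRGlu 0.8 SD, unrelated to HDRS change | 4.9% | 5.0% | 9.2% | 4.9% | 97.8% | 5.3% |
| No effect on MRGlu, r = 0.39 in both arms | 81.3% | 82.1% | 30.4% | 98.3% | 4.9% | 5.1% |
| No effect on MRGlu, r = 0.27 in both arms | 48.1% | 47.7% | 49.4% | 77.5% | 5.0% | 5.0% |

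In the first row a large effect on metabolism leaves every planned correlation at its false-positive rate. In the other rows the arms are identical, yet one is significant and the other not in 30% to 49% of trials. Arithmetic check for the second row: 0.813 × 0.179 + 0.187 × 0.821 ≈ 0.30.

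**3. The pooled correlation.** With zero within-arm correlation, equal arms, and shifts a in MRGlu change and b in HDRS change, pooled r = (ab/4)/√((1 + a²/4)(1 + b²/4)).
- a = 0.8, b = 0.5: 0.10/√(1.16 × 1.0625) = 0.09. Significant in about 15% of simulated trials.
- a = b = 0.8: 0.16/1.16 = 0.14. Significant in about 28%.

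The pooled analysis therefore responds somewhat to a mean shift if HDRS shifts too, but here it reports an association that exists within neither arm.

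**4. Detectable between-arm difference in MRGlu.** A two-sample t-test with 50 per arm detects 0.566 SD of whatever is compared. On one common scale, SDs of post-treatment MRGlu, with equal pre and post SDs and pre-post correlation ρ (assumed):
- change score: 0.566 × √(2(1 − ρ))
- ANCOVA on baseline: 0.566 × √(1 − ρ²)

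| ρ (assumed) | Change score | ANCOVA |
|---|---|---|
| 0.5 | 0.57 | 0.49 |
| 0.7 | 0.44 | 0.40 |
| 0.8 | 0.36 | 0.34 |

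**5. Detectable difference between correlations.** SE = √(2/47), so the Fisher z difference needed is 2.802 × √(2/47) = 0.578. That corresponds to 0.52 against 0, or 0.65 against 0.20. Power for 0.39 against 0 is 51%.

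**The case against.** The best defence is that Aim 2 is correlational by design. In section E the effect-of-treatment clause completes a sentence whose subject is the correlation with HDRS change, so it may ask only whether that correlation differs by arm. Section A labels treatment-specificity exploratory. Both points stand: the main hypothesis test is untouched, and an exploratory question needs no confirmatory apparatus. But the narrower reading also lacks a test, and the exploratory label does not make an uninformative statistic informative.

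Three stronger readings are tempting, and the documents do not support them.

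- A reader might infer that the plan makes a causal claim about the SSRI specifically. The sentence in section A covers SSRI or placebo alike and concerns only the outcome in which no correlation is found.
- A reader might infer that the planned analyses have no power at all against a mean shift. That is exact within an arm but false for the pooled correlation, as step 3 shows.
- A reader might infer that the placebo arm was justified as a control for time and repeat-scan effects. Section A names only the placebo effect.

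It is also fair to object that a completer comparison may not be fully randomised. Section D removes treatment-group subjects who worsen or respond inadequately, and section G drops subjects who worsen, so missing week-8 scans may differ by arm. This stands, and it limits what the added model can claim.

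**Conclusion.** The point holds for the exploratory treatment-specificity question and for the mechanistic reading built on it. It does not touch the main correlational hypothesis. The gap lies in the written analysis, not the design, because both randomised arms are to be scanned at week 8.

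The 30% discordance assumes a common true correlation of 0.39 and 50 completers per arm; it rises to 49% at 0.27. The detectable MRGlu differences rest on the assumed pre-post correlations, equal SDs and 50 completers per arm with week-8 scans. Power for either added comparison is modest, so a null result would not show that the drug has no effect on MRGlu. The change is worth making before the data are analysed.

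**What to change.** Keep the correlations of MRGlu change with HDRS change as the symptom analysis. In section E, Aim 2, replace the effect-of-treatment clause with text to this effect:

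> Exploratory: (a) the ESC minus placebo difference in week-8 MRGlu will be estimated in each Aim 2 region from a linear model with arm and baseline MRGlu, with 95% CI. (b) Whether the relation between MRGlu change and HDRS change differs by arm will be assessed by an arm-by-MRGlu-change interaction, not by comparing the significance of separate correlations. Changes will be described as due to SSRI rather than placebo only on the basis of (a). Missing week-8 scans will be reported by arm, with reasons.

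Part (b) is needed only if that is the intended question. Before (a) is fixed, reconcile the regions: section A names frontal cortical areas, section E a midbrain cluster. Report all regions with their intervals, as befits an exploratory analysis, and state the detectable differences above. The figures 0.39 and 0.27 should not be cited as power for either comparison. Describe (a) as a comparison of subjects with a week-8 scan, given the removals in sections D and G.

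The cost is one extra model per region for (a), one interaction term if (b) is wanted, and a few lines of text. No patients, scans or procedures are added.

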COMMITTEES ON RESEARCH INVOLVING HUMAN SUBJECTS Established 1971

Protocol Summary Form

TITLE: Advancing Personalized Antidepressant Treatment Using PET/MRI **INVESTIGATORS:** [name] Co-Investigators: [name], PhD, [name], [name], [name], [name], [name], [name] [name], [name], PhD, [name], PhD **Department**: Psychiatry

A. SPECIFIC AIMS:

Despite the burden of failed trials, there are currently no tools for treatment selection in Major Depressive Disorder (MDD). Referring to a recent Positron Emission Tomography (PET) study using 2-[¹⁸F]-fluorodeoxyglucose (FDG), NIMH Director [name] remarked that PET imaging is "on the cusp" of aiding in MDD treatment decisions. To finally realize this goal, the limitations of previous FDG studies must be addressed, including limited sample size, lack of placebo comparison (the placebo effect is a significant obstacle to evaluating treatment mechanism and efficacy), and use of relative outcome measures. In the proposed study, FDG imaging before and after Selective Serotonin Reuptake Inhibitor (SSRI) treatment will be performed using a simultaneous PET/Magnetic Resonance (MR) scanner and: (1) the largest sample size to date; (2) a placebo group; and (3) full quantification using analysis of FDG activity in plasma, which yields more accurate estimates of metabolism than relative activity.

Aim 1: Determine a Pretreatment Marker of SSRI Effectiveness Using PET. With the goal of reducing MDD burden, many studies have assessed the utility of FDG-PET in antidepressant treatment prediction. However, due to the limitations listed above, there is no consensus on which brain regions are predictive of treatment efficacy. In addition to serving as a biomarker of SSRI effectiveness, only conclusive determination of these regions will provide insight into depression pathophysiology, helping uncover SSRI mechanism of action, and aiding in the search of novel therapeutics. Based on our preliminary data and other, similar studies, we hypothesize that SSRI-induced change in the Hamilton Depression Rating Scale (Δ HDRS) will be correlated with pretreatment metabolic rate of glucose (MRGlu, quantified using arterial blood analysis) in three potential regions: (1) midbrain, (2) right anterior insula, and/or (3) left ventral prefrontal cortex.

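### Aim 3 can declare that SimE matches arterial MRGlu without testing mean bias, and no rule keeps one method within an Aim 2 change score

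*Combined protocol and SAP*

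**What the plan says.** Section E, Aim 3 sets the end point of the validation: "Validation will be considered complete when MRGlu using conventional (Patlak) analysis and arterial samples matches MRGlu calculated with SimE and one venous sample". The criterion follows: "The threshold will be a correlation of at least 0.95 and slope of 0.85 in at least 30 subjects". The pilot result, with a blood sample at 40 minutes as anchor, is "slope 0.876, correlation 0.974 with Patlak analysis"; against compartmental analysis it is slope 0.730 and correlation 0.955. No intercept or mean difference is reported. The plan does not say whether the slope is fitted with an intercept, which variable is regressed on which, whether 0.85 is a minimum, or whether the unit is the subject, the scan or the region.

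Section A presents absolute level as the advantage of the measure: "full quantification using analysis of FDG activity in plasma, which yields more accurate estimates of metabolism than relative activity". Of the noninvasive method it says "SimE fully quantifies brain MRGlu without requiring an arterial catheter".

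For Aim 1, section A describes pretreatment MRGlu as "quantified using arterial blood analysis". Section D, however, continues a scan when the arterial line cannot be placed, and analyses it with the SimE anchor. Its remark on consistency covers only a line not used at baseline, and says only that the follow-up will likely go the same way. Under Image Processing, section D derives SimE alongside the arterial result for comparison. Section E names no quantification method for the Aim 2 change, and does not say how SimE-only scans enter Aims 1 and 2.

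**The concern.** Correlation and slope describe how SimE values move with arterial values. Agreement in level is a separate property, and it is the one that full quantification claims. A rule that leaves level untested could call the method validated although every value is shifted, and others could then drop the arterial line on that basis.

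The same untested shift could reach Aims 1 and 2. If one method is used throughout, a common offset or slope leaves the correlations unchanged. If an arterial baseline is subtracted from a SimE follow-up, any level difference enters that subject's change score and dilutes its correlation with change in HDRS.

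**Working it through.** **1. The plan's own figures.** The Aim 3 threshold has no stated derivation, so there is nothing to reproduce. The Aim 2 power statement, used in step 5, does reproduce: minimum r = tanh((1.960 + 0.842)/√(50 − 3)) = 0.387, stated as 0.39. Power at r = 0.39 is 80.6%.

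**2. Effect of a constant shift.** Write SimE = a + b·x + e, with x the arterial value. Replacing a by a + c leaves the correlation and the free-intercept slope unchanged, and moves the mean by c. Thirty constructed pairs, with mean arterial MRGlu scaled to 100 and an assumed CV of 20%, show this:

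| Offset | r | Slope, with intercept | Mean bias | Slope through origin | Lin's concordance |
|---|---|---|---|---|---|
| −40 | 0.950 | 0.850 | −55% | 0.465 | 0.18 |
| −20 | 0.950 | 0.850 | −35% | 0.657 | 0.35 |
| 0 | 0.950 | 0.850 | −15% | 0.850 | 0.72 |
| +15 | 0.950 | 0.850 | 0% | 0.994 | 0.94 |
| +30 | 0.950 | 0.850 | +15% | 1.139 | 0.72 |
| +60 | 0.950 | 0.850 | +45% | 1.428 | 0.25 |

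All six cases pass with a free intercept. Through the origin, with 0.85 as a minimum, the first two fail and the other four pass.

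**3. Chance of passing.** Inputs: true slope 0.876 and r 0.974 (section E), n = 30, one value per subject, CV 10-30% (assumed), residual SD = b·CV·√(1 − r²)/r. Studies were simulated, and a pass means r ≥ 0.95 and slope ≥ 0.85.
- Free intercept: about 73-74% at mean bias 0%, −12.4%, +20% and −30% alike. The −12.4% is the zero-intercept case, 0.876 − 1.
- Through origin: 0% at bias −20% and −30%; about 96-97% at −12.4%, 0% and +20%.

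**4. Can the planned data measure the bias?** SD of the paired difference = CV·√[(1 − b)² + b²(1 − r²)/r²] = CV·√(0.0154 + 0.0415) = 0.2385·CV. At n = 30 the 95% CI half-width is 2.045 × 0.2385·CV/√30, or about 0.9 points at CV 10% and 2.7 at CV 30%. Limits of agreement are 1.96 × 0.2385·CV, about ±5 to ±14 points around the bias.

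**5. Mixed change score (Aim 2).** Assumed: CV 15%; SD of true change s = 5, 10 or 15% of the mean; a share p of subjects with SimE follow-up minus arterial baseline; residuals independent between scans. From the plan: n = 50, true r 0.39, b = 0.876. Residual SD = 0.876 × 0.15 × √(1 − 0.974²)/0.974 = 0.0306.
- Mixed change = a + (b − 1)x₁ + b·D + e, where x₁ is the arterial baseline and D the true change. Its mean is −0.124 with zero intercept and 0 with equal means.
- Observed r = 0.39·s·(1 − p + p·b)/√V, where V = (1 − p)s² + p[(0.124 × 0.15)² + b²s² + 0.0306²] + p(1 − p)·mean².
- Example (p = 20%, s = 5%, zero intercept): numerator 0.0195 × 0.9752 = 0.01902; V = 0.00200 + 0.00064 + 0.00246 = 0.00510; r = 0.266; power about 46%.

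| Power (80.6% unmixed) | s = 5% | s = 10% | s = 15% |
|---|---|---|---|
| 2% mixed, zero intercept | 75% | 79% | 80% |
| 20% mixed, zero intercept | 46% | 69% | 75% |
| 20% mixed, equal means | 76% | 79% | 80% |
| Same 20%, SimE at both scans | 74% | 79% | 80% |

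If the residuals correlate 0.7 between scans, SimE at both scans gives 78% rather than 74% at s = 5%.

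**6. Pooling in Aim 1.** With 10 of 50 subjects SimE-only and zero intercept, unadjusted pooling gives 70-79% power over CV 10-20%. Recalibrated values give about 81%, and arterial-only (n = 40) gives 71-72%.

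**The case against.** - **The slope may be a bias tolerance.** With a zero intercept, 0.85 is an openly stated allowance of up to 15%, set beside a disclosed pilot slope of 0.876. No passage reports an additive offset. This stands as far as it goes: the plan hides nothing, and offsets other than zero are constructed here. But the plan reports no intercept, so the allowance is on level only if the intercept is zero, and nothing in the rule tests that.
- **A through-origin fit would respond to level.** Correct. A reader might infer that the rule is blind to mean bias under any reading. The documents do not support that, because the form of the fit is unstated. What remains is that the through-origin reading is one-sided and still passes a 12% underestimate.
- **Section D does not prescribe mixing.** Also correct. A reader might infer that an arterial baseline with a failed follow-up line must give a mixed change. Section D says only how the scan without the line is analysed. SimE is derived for the other scans as well, so a same-method change is available, and consistency is the stated aim. Mixing is possible by omission.
- **The power losses rest on assumptions.** They do. The 46% needs 20% mixed, zero intercept and a small SD of change together. With equal means, mixing costs little and at 20% does up to 2 points better than SimE at both scans.

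**Conclusion.** The Aim 3 point holds and does not depend on how often lines fail. As written, the rule can declare a match at any mean bias if the slope has an intercept, and at an underestimate of about 12% or any overestimate if it does not. A pass would show that SimE tracks arterial MRGlu, which falls short of showing that it can replace arterial sampling for absolute values. The 73-74% pass chance assumes that the pilot slope and correlation are true, with one value per subject.

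It would go too far to say that SimE is biased by 12.4%: that figure follows only from a zero intercept, and no intercept is given.

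The Aim 2 point is secondary, a missing rule whose effect is unknown. Over the assumed ranges, power falls from about 81% to 75-80% at 2% mixed and 46-75% at 20% mixed with zero intercept, and to 76-80% at 20% mixed with equal means. The Aim 1 and 2 correlations are not at risk from a common offset or slope where one method is used throughout.

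**What to change.** **Aim 3.** Keep the correlation and slope thresholds. State the fit (with intercept), the direction (SimE on arterial) and the unit of analysis. Add mean percent bias with a 95% CI and Bland-Altman limits of agreement. Say that SimE matches only if the CI for mean bias lies within a margin that the sponsor fixes before the comparison is run. Otherwise report it as correlated with arterial MRGlu but needing recalibration.

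**Aim 2.** Form each subject's change with one quantification method at both scans. Where a scan has arterial but no venous blood, its 40-minute arterial sample could serve as anchor, since section E says "FDG venous and arterial samples are essentially interchangeable" at that time.

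**Aims 1 and 2.** Where SimE-only values or changes are combined with arterial ones, recalibrate them on this trial's paired scans, and report the arterial-only result as a sensitivity analysis.

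**Cost.** Wording and little computation, since both measures are already derived. A validated result becomes harder to reach, but the data can decide it. For illustration, at n = 30 with equal means a 5% margin is met in 91-100% of simulated studies and a 10% margin in all; with zero intercept neither is met. SimE at both scans for 20% of subjects costs about 2 power points at SD of change 10%, and about 7 at 5%. Recalibrating those changes puts them on the arterial scale but also enlarges their residual error. At SD of change 5%, V = 0.8 × 0.0025 + 0.2 × [0.0025 + 2 × (0.0306/0.876)²] = 0.0030, r = 0.0195/√V = 0.357, and power is about 73% rather than 74%.
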